### 2. SCHEMA

Study sequence is shown above for all steps following informed consent in Visit 1.

- Subjects who meet the inclusion criteria are first asked to keep a symptom diary for two weeks to determine whether they have an adequate amount of staining, solid or liquid fecal incontinence to be enrolled. The number of FI episodes during baseline will become the reference for judging whether they demonstrate a 75% reduction in the frequency of FI. For patients who have a variable pattern of FI and the investigator believes that the initial two-week diary data collection did not adequately capture the extent of the FI, then the baseline bowel diary may be kept by the patient for an additional two weeks.
- 2. Subjects who have an adequate amount of FI during baseline and who fulfill other inclusion criteria are enrolled in a 4-week EMM protocol to determine whether this will reduce their FI episodes by 75% or more. If it does, they are not included in the randomized trial but are scheduled to return at 3 months for a follow-up assessment. If the subject does not achieve at least a 75% reduction in FI, they are randomized to one of two therapies: BIO or INJ. Whether or not participants are EMM responders, data regarding ongoing adherence to the EMM prescriptions will be collected from participants at the end of the 1-month EMM period and then also at the 3-; 6-; 12-; and 24-month follow-up assessments.
- 3. Each treatment intervention follows a printed protocol document. The number of treatment visits varies somewhat, from 2-3 visits for INJ, and 5-6 visits for BIO.

At 3 months, all subjects who received a randomized therapy are assessed to determine whether they meet the criteria for treatment success. If they fail to demonstrate a 75% decrease in FI compared to baseline, they are labelled as treatment failures and are offered the opportunity to try the other randomization treatment or SNS. Those subjects who were initial responders to EMM but who are determined at 3 months follow-up to no longer be responding to EMM will be eligible to be randomized to one of the two treatment therapies (BIO or INJ). For all participants, follow-up assessments occur at 6, 12, 18 and 24 months. The 3-, 6-, 12 and 24-month follow-up assessments may be completed in-person or remotely. The more limited follow-up data collection at 18-month should always be collected during a telephone call.

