- C. Identify baseline predictors of responsiveness to each intervention and the mechanistic basis for each treatment. Candidate predictors are (a) demographic variables (e.g., sex, age, race, ethnicity, education); (b) clinical history variables (e.g., FI frequency, volume, duration, and association with urgency and diarrhea); and (c) baseline pelvic floor physiology (e.g., anal canal resting pressure, squeeze pressure, duration of squeeze, rectal sensory threshold for first sensation and urgency, maximum tolerable volume, structural integrity of anal sphincters assessed by ultrasound, and integrity of the pelvic floor innervation by trans-sacral and trans-lumbar magnetic evoked potentials).

- D. Evaluate treatment combinations. Patients who do not meet the responder criterion by 3 months follow up will be offered the option of choosing additional therapy. This constitutes a pragmatic clinical trial which mimics clinical practice and will provide preliminary data for a future study. A second reason for allowing patients to add an additional preferred treatment if they do not show at least a 75% improvement is to facilitate recruitment; in our feasibility survey, subjects told us that the opportunity to try another treatment if the first failed would increase their willingness to be randomized. Data analysis will estimate 95% confidence intervals for the percent of responders to each treatment combination and to each monotherapy, and differences in responder rates between groups will be assessed.
  - Research objective 4. To compare the improvement in FI after combination treatment versus monotherapy and compare improvement among various treatment combinations, up to 24 months after administration of each treatment combination, compared to monotherapy.
  - Research objective 5. To estimate differences in the magnitude of improvement in FI from baseline to end of treatment between the treatment combinations.
- E. Assess the efficacy and durability of enhanced medical treatment and identify patient characteristics that predict treatment response.
  - Research objective 6. To estimate the responder rate during the last two weeks of enhanced medical treatment and also during follow up at 3, 6, 12, and 24 months.
  - Research objective 7. To assess the proportion of patients reporting AEs of pelvic pain of grade II or higher, or SAEs requiring hospitalization, during all weeks of medical treatment.

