### 4.0 Outcome Measures

4.1 Primary Outcomes: There are three primary outcomes: efficacy, safety, and cost.

*4.1.1 Efficacy:* The primary efficacy analysis will be based on the proportion of responders in each treatment arm. A responder will be defined as an individual whose symptom diaries demonstrate at least a 75% reduction in the average weekly frequency of FI from baseline (prior to the EMM to the last two weeks of the treatment period preceding the 3-month post intervention follow up. The rationale for choosing a 75% reduction in the frequency of staining, solid and liquid stool incontinence as the primary outcome measure is that, both in focus groups and surveys we conducted, half of patients with FI reported that they did not consider a 50% reduction in FI episodes to be a satisfactory measure of treatment success; rather, they believed an improvement of 70-80% was necessary for a treatment to be considered successful.

The frequency of FI will be recorded on a paper diary. Patients will be asked to record (1) the time of each accidental bowel leakage (ABL), (2) the amount of leakage that occurred, (3) the rectal sensation that occurred prior to the event (no awareness, normal warning, or strong urge), and (4) the consistency of the leaked stool. Patients will also be asked to record (5) the time of any BM that occurred in the toilet even if this starts as an ABL and is finished by passing stool in the toilet, (6) the consistency of the BM using the Bristol Stool Form Scale, and (7) medications or other treatments employed. The primary outcome is based only on the number of FI events; however, the amount of stool lost and the type of sensation experienced before the leakage are needed to guide the BIO intervention, and the number and consistency of BMs and use of fiber or medications is used to guide the EMM intervention. Rather than use different diaries for each of these purposes, we will ask all subjects to use this paper diary throughout the intervention period and for two-week periods preceding all follow up assessments.

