#### 5.1 Inclusion/ Exclusion criteria

Inclusion Criteria	Exclusion Criteria
Physician diagnosis of FI (R15) for the past 6 months or longer. We will recruit some subjects by advertisement who may not have consulted a physician, and this diagnosis may be made by the study physician. Able to ambulate independently on level surfaces. Patient may use	Dementia will be assessed using the Six-Item Screener to Identify Cognitive Impairment. The subject is asked to remember 3 words (apple, table, penny), which may be repeated up to 3 times. This is followed by 3 questions on the year, month, and day of the week. Finally, the subject is asked to recall the three words. Three or more errors has a sensitivity of 88.7% and specificity of 88.0% compared to clinical diagnosis and is not different from the Mini Mental State Exam. [Callahan, CM et al. Six-Item Screener to Identify Cognitive Impairment among Potential Subjects for Clinical Research. Medical Care 2002;40:771-81.] Obstetrical injuries including third and fourth degree tears in the anal sphincter within 6 months.
assistive devices other than parallel bars.	
Average ≥2 solid, liquid, or staining FI episodes per week by self-report and during the two-week baseline	Pregnant or planning pregnancy in next 2 years
Meets criteria for dextranomer treatment except an internal anal sphincter defect of 180 degrees or less is acceptable.	Internal anal sphincter separation >180 degrees on ultrasound or magnetic resonance imaging
Required for randomization: Less than 75% reduction in the number of FI episodes after 4 weeks of EMM.	Spinal cord injury or spina bifida
Age >=18 years	Congenital malformation of anorectum
	Complete rectal prolapse or grade III/IV hemorrhoids
	History of ileoanal pouch; history of anal sphincteroplasty, rectopexy, or rectocele repair within the past 6 months; or history of pelvic surgery with synthetic graft and suspected graft erosion into the anus, rectum, or skin or if the graft ends less than approximately 1" above the upper limit of the anal canal.
	Established diagnosis of inflammatory bowel disease
	Intestinal stoma present
	History of pelvic radiation within previous 12 months or presence of active radiation proctitis.
	Patients who cannot expel the rectal balloon during the balloon expulsion test and who have constipation most of the time.
	Anatomic limitations to placement of dextranomer injections.
	Presence of existing implant in the anorectal region

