#### 8.3 Analysis of Secondary Aims

*Identify predictors of treatment response to each intervention.* Generalized linear modeling will be used to identify baseline variables which are significant independent predictors of responder status at 3 months. Candidate independent variables in these models include (a) demographic variables (e.g., sex, age, race, ethnicity, education); (b) clinical history variables (e.g., FI frequency, volume, duration, and association with urgency and diarrhea); and (c) baseline pelvic floor physiology (e.g., anal canal resting pressure, squeeze pressure, duration of squeeze, rectal sensory threshold for first sensation and urgency, maximum tolerable volume, structural integrity of anal sphincters assessed by ultrasound, and integrity of the pelvic floor innervation by trans-sacral and trans-lumbar magnetic evoked potentials) and other moderator variables described in the protocol. Differences in predictors of response among the treatment groups will be assessed by evaluating interaction terms for the predictors and treatment group. Secondary analyses evaluating predictors of treatment response at other time points and predictors of other secondary outcomes will be conducted using similar methods.

Investigate the mechanistic basis for treatment success for each intervention. General linear modeling will be used to identify measures associated with change from baseline to 3 months in FI frequency. The independent variables to be tested are anal squeeze pressures, rectal sensory thresholds, rectal maximum tolerable volume, trans-lumbar and trans-anal magnetic evoked potential, stool consistency measure by the Bristol Stool Form Scale, and adherence to protocol. Differences in predictors among the treatment groups will be assessed by evaluating interaction terms for the predictors and treatment group.

*Evaluate treatment combinations.* To assess the effectiveness of allowing non-responders to choose an additional treatment at 3 months, we will estimate 95% confidence intervals for the number of responders in each treatment-order combination at 6, 12, and 24 months using a Wilson Score interval. Confidence intervals will be compared descriptively.

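### Section 8.3 tests baseline FI frequency as a predictor of a response that is scored against, in all likelihood, the same diary count, so it can look predictive when it is not

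*Combined protocol and SAP*

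**What the plan says.** Aim C in Section 1.1 is to "Identify baseline predictors of responsiveness to each intervention and the mechanistic basis for each treatment". Section 8.3 carries this out with generalized linear models meant to find "significant independent predictors of responder status at 3 months". The candidates include "clinical history variables (e.g., FI frequency, volume, duration, and association with urgency and diarrhea". The same section plans predictor-by-treatment interaction terms and extends the methods to other time points.

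The outcome is defined elsewhere. Section 4.1.1 makes a responder someone with "at least a 75% reduction in the average weekly frequency of FI from baseline", and item 1 of the Schema in the Protocol Summary says "The number of FI episodes during baseline will become the reference for judging whether they demonstrate a 75% reduction". The baseline diary is also used for entry in Section 5.1, "Average ≥2 solid, liquid, or staining FI episodes per week by self-report and during the two-week baseline", and for the randomization filter, "Less than 75% reduction in the number of FI episodes after 4 weeks of EMM", which Section 7.1 ties to the same two-week baseline.

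Section 8.3 does not say which instrument supplies FI frequency. Nor does it say how an association between a baseline count and an outcome scored against a baseline count is to be read.

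**The concern.** Let B be the baseline two-week count and F the follow-up two-week count. Response is the event F ≤ 0.25 × B. If the predictor is B, it stands on both sides of the model. A fortnight that happens to be bad raises the predictor and loosens the target for the same patient. A slope can therefore arise although treatment lowers every patient's true rate by a proportion that has nothing to do with severity.

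At stake is one named result of a specific aim. The trial could report that more frequent FI predicts response, in one arm or both, when the finding is arithmetic. Because Section 8.3 repeats the method at later time points, the same slope could recur there and be taken for confirmation.

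**Working it through.** **1. Sample size used.** The plan gives no figure for the predictor analysis, so the relevant figure is the number randomized. Section 5.2.1 assumes a 20-point difference around 50% (taken as 40% against 60%), alpha 0.05 (taken as two-sided) and 80% power:

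n = [1.960 × √(2 × 0.5 × 0.5) + 0.842 × √(0.4 × 0.6 + 0.6 × 0.4)]² / 0.20² = (1.386 + 0.583)² / 0.04 = 96.9, so 97 per group and 194 in all. This agrees with the plan.

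**2. The shared count.** The largest F that still counts as response is B/4 rounded down: 1 for B = 4 to 7, 2 for B = 8 to 11, 3 for B = 12 to 15. As an illustration, assume two patients with the same true rate of 6 per fortnight and the same true 75% reduction, so F is Poisson with mean 1.5. One happens to record 6 at baseline, the other 8.

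- B = 6: P(F ≤ 1) = e^(−1.5) × (1 + 1.5) = 0.223 × 2.5 = 56%.
- B = 8: P(F ≤ 2) = 0.223 × (1 + 1.5 + 1.125) = 0.223 × 3.625 = 81%.

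Across patients a higher B also signals a higher true rate, which pulls the other way. The net effect needs simulation.

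**3. Simulation under no true association.** From the documents: 194 patients, 1:1 allocation, entry at 4 or more episodes in two weeks, less than 75% reduction on EMM, response as above. Assumed: log-normal true weekly rates (median 3.5, log-SD 0.6; alternatively 6 and 0.7), a true proportional effect independent of that rate, and Poisson or gamma-Poisson counts with period-to-period CV from 0 to 0.8. The model is logistic, response on arm and log B, with a Wald test at 0.05 and 400 trials per row. The Monte Carlo standard error at 5% is √(0.05 × 0.95 / 400) = 1.1 points.

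| Median rate per week | CV | False positives, main effect | Odds ratio per doubling | Response, lowest vs highest third of B | False positives, interaction |
|---|---|---|---|---|---|
| 3.5 | 0 | 8% | 1.07 | 52% vs 56% | 4.5% |
| 3.5 | 0.3 | 18% | 1.20 | 52% vs 60% | 4.0% |
| 3.5 | 0.5 | 31% | 1.32 | 52% vs 63% | 4.3% |
| 3.5 | 0.8 | 58% | 1.47 | 55% vs 70% | 2.2% |
| 6 | 0 | 6% | 1.07 | 50% vs 54% | 4.3% |
| 6 | 0.3 | 19% | 1.19 | 48% vs 57% | 5.2% |
| 6 | 0.5 | 42% | 1.30 | 46% vs 61% | 4.8% |
| 6 | 0.8 | 72% | 1.44 | 46% vs 66% | 4.0% |

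With arms of unequal true effect (median 3.5), main-effect false positives were 5%, 13%, 29% and 48% at the four CVs, and the interaction stayed between 4% and 6%.

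A separate null simulation at N = 194 gave odds ratios of about 1.0, 1.15, 1.3 and 1.45, false positives of about 5%, 10–14%, 28–44% and 52–76%, and 3–7% for the interaction. A model with gamma-distributed rates (mean 10 per fortnight) gave 1.05, 1.24, 1.43 and 1.56, with 5%, 20%, 54% and 84%. The upper end therefore depends on the model and is not a bound.

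**4. Where the excess comes from.** When response was scored on true rates instead of counts, the same test rejected in 3% to 7% of trials. The shared count is the cause.

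**5. Role of the entry criterion.** Without the entry threshold (any B above 0, median 3.5), false positives rose to 52%, 81% and 92% at CV 0.3, 0.5 and 0.8. The threshold removes patients with 1 to 3 baseline episodes, whose limit would be zero, so it weakens the artefact.

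**6. Substitute predictors.** An independent second two-week diary as predictor, with the first still used for entry and response, rejected in 10% to 27% of null trials, with odds ratios of 0.80 to 0.92. With the end-of-EMM diary as predictor and EMM benefit continuing into the treatment period, odds ratios were 0.72 to 0.93 and false positives reached 49%.

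**The case against.** **The source is not stated.** FI frequency sits under clinical history. Frequency is also self-reported at entry (Section 5.1) and enters the FISS (Section 4.2.1), and where the plan wants a diary-derived moderator it says so (Section 4.3.4, passive versus urge FI). This stands in part. The Synopsis says that the frequency of FI is measured with the diary and also lists FI frequency as a predictor, so the diary is the natural reading, but it remains a reading.

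**The artefact may be small.** With pure Poisson counts it nearly vanishes. This stands, and a reader who infers that baseline frequency is bound to look predictive goes further than the documents allow. They give no within-patient variability. They do say that some patients have a variable pattern of FI and allow a further two weeks of baseline diary for them (Synopsis), which makes the Poisson case the least plausible. That extension was not simulated.

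**The entry criterion is not a cause.** A reader might blame it because it uses the same diary. Step 5 shows the opposite for this predictor.

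**Treatment choice is not misdirected.** Choosing between BIO and INJ rests on the interaction, which is already planned and keeps about its nominal error rate. A slope common to both arms favours neither. This stands, and it limits the harm to the main-effect claim.

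**Other predictors.** A reader might also infer that urgency or loose stools are distorted through their correlation with B. No calculation here supports that.

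**Conclusion.** The concern holds in a conditional form. If FI frequency in Section 8.3 is the pre-EMM diary count, its main effect on the 75% responder outcome is coupled with the endpoint, and the plan has no safeguard. For an assumed within-patient CV of 0 to 0.8, the null odds ratio per doubling is about 1.0 to 1.5 and the false-positive rate at N = 194 about 5% to 76%, always towards better apparent response at higher baseline frequency. One alternative rate distribution reached 1.56 and 84%. These figures rest on assumed rate distributions, a proportional benefit unrelated to severity, and complete diaries; counting missing diaries as non-response was not modelled.

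The interaction with treatment stays at about 2% to 7%. The primary efficacy comparison, which adjusts only for site and sex (Section 8.1), and its 97 per group are untouched.

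**What to change.** In Section 8.3:

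- State that FI frequency as a candidate predictor is the pre-EMM two-week diary count.
- Make no significance claim for its main effect on the 75% responder outcome at any time point. Report it descriptively, labelled as coupled with the endpoint.
- Base conclusions about FI frequency on its interaction with treatment.

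Do not present the Randomize (end-of-EMM) diary as an unbiased replacement. Response is still scored against the pre-EMM baseline, all participants are encouraged to continue EMM (Section 3.0, item 8), and the end-of-EMM count decides who is randomized. It therefore carries EMM response and selection. For initial EMM responders randomized after relapse (Section 3.0, item 2), it also shows their earlier response and not their state before randomized treatment. If the sponsor means some other source, the plan should name it and treat its main effect with the same reserve, since even an independent diary missed the 5% level.

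The change takes two or three sentences and no new data. The price is that the trial gives up a formal test of the main effect of baseline frequency.

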#### 5.4 Estimated patient flow for this study

Figure 3 shows the estimated flow of patients through this study and identifies our assumptions regarding attrition. We estimate we will need to screen 855 patients because 2/3 will be ineligible or unwilling to be randomized. This leaves 285 to be recruited into the EMM protocol. Based on the Heymen study, we assume

15% attrition during this treatment phase and also assume that 20% (n=57) will be responders to EMM and therefore not eligible for randomization. This will leave 194 to be randomized (97 per group).

Figure 3 shows that we expect 78 from the BIO group to complete the 3-month assessment after allowing for attrition of 20% and we expect 92 from the INJ group to complete the 3-month assessment. (We assume attrition will be no greater than 5% for the INJ group because this is a low-burden treatment and also because patients will want to be screened for AEs related to INJ.) However, the statistical analysis will be by intent to treat (ITT) and will include all 194 randomized to treatment; patients who are lost to follow up prior to 3 months will be considered treatment failures. The number of patients we expect to be responders to each of the treatments at the 3-month assessment is based on the pivotal trials shown in Table 1. We separated them in this way in Figure 3 to be able to estimate the numbers of non-responders who are likely to choose an additional treatment option after 3 months. The expected number of non-responders eligible for an additional therapy at 3 months is 63 for the INJ arm^16 and 17 for the biofeedback arm^15. Assuming equal probability of choosing either of the 2 available options as an added or alternative treatment, we could expect 40 patients to choose the SNS treatment, 32 to choose BIO, and 9 to choose INJ. For the primary analyses of follow up at 6, 12 and 24 months, these non-responders will be retained in the ITT analysis as non-responders to their primary assignment at randomization. However, when we perform exploratory analyses of treatment combinations, these subjects will be treated as distinct groups and compared to patients who received monotherapy for the duration of the study. These comparisons (Aim D) are exploratory because there is insufficient power to test for significance. The left column of boxes in Figure 3 shows how we intend to follow up the responders to EMM.

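### Section 8.3's mechanistic model of change in FI frequency names no scale and omits baseline FI frequency, so a marker of severity can pass for a mechanism

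*Combined protocol and SAP*

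**What the plan says.** The mechanistic paragraph of Section 8.3 (Combined protocol and SAP) reads: "General linear modeling will be used to identify measures associated with change from baseline to 3 months in FI frequency". Its variable list begins: "The independent variables to be tested are anal squeeze pressures, rectal sensory thresholds, rectal maximum tolerable volume". It continues with evoked potentials, stool form and adherence, and adds interactions with treatment group. The paragraph gives no scale for change, no transformation, no count model and no baseline FI frequency term. It does not say whether the physiological measures enter as baseline values or as changes.

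The paragraph on predictors in the same section works differently: "Generalized linear modeling will be used to identify baseline variables which are significant independent predictors of responder status at 3 months". Its candidates include "clinical history variables (e.g., FI frequency, volume, duration, and association with urgency and diarrhea". So that analysis has a relative outcome and baseline frequency is available to it.

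Section 4.1.1 defines a responder by "at least a 75% reduction in the average weekly frequency of FI from baseline". Section 5.1 requires "Average ≥2 solid, liquid, or staining FI episodes per week by self-report and during the two-week baseline", which is a minimum with no maximum on FI episodes.

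**The concern.** Absolute change is the natural reading for two reasons. Section 8.2 uses the same expression for FISS, FIQOL and PROMIS score changes, and the plan states a percentage when it means relative change.

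Absolute change in a count is bounded by the baseline count. The entry minimum of 2 per week is 4 episodes in a two-week diary, so such a participant can lose at most 4, while one with 30 can lose 30. For a participant who becomes continent, the absolute change is the baseline count itself. For any 75% responder it lies between 75% and 100% of baseline. Table 3 expects 78% of BIO and 32% of INJ patients to reach that level.

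Without a baseline term, a squeeze, sensory or stool-form measure that merely accompanies more severe disease can therefore be associated with the outcome. At stake is the mechanistic part of Aim C. It could label a severity marker as a mechanism, miss some real ones, and disagree with the responder-based models in the same section.

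**Working it through.** **The plan's own figure.** The documents give no power or error rate for this analysis. The only sample size that can be reproduced is the primary one, 40% vs 60% at two-sided 0.05 and 80% power: n = (1.96·√(2·0.5·0.5) + 0.8416·√(0.4·0.6 + 0.6·0.4))² / 0.2² = (1.386 + 0.583)² / 0.04 = 96.9, so 97 per group, as Section 5.2.1 states. It does not bear on this point.

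**Why the association arises.** Write B for baseline frequency, p for the proportion improved and x for the measure. Absolute change is B·p. If p is independent of B and x, then cov(x, B·p) = E(p)·cov(x, B). This is non-zero whenever x is correlated with B, although x has no bearing on p.

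**Inputs from the documents.** Section 5.4 says "we expect 78 from the BIO group to complete the 3-month assessment" and "we expect 92 from the INJ group to complete the 3-month assessment", so n = 78 + 92 = 170. The 75% responder rates are 78% (BIO) and 32% (INJ), from Tables 1 and 3. Section 4.3.7 has evoked potentials at two of five sites, so n = 80 was also run.

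**Assumed inputs.** Table 3 gives a spread only for FI days (3.4 per week, SD 2.1, biofeedback trial), so the spread of episodes had to be assumed.
- Baseline rate: 2 plus a lognormal, with mean/SD of 4.8/2.1, 6/4 or 8/8 episodes per week.
- Diaries: two-week Poisson counts, with baseline at least 4.
- Log rate ratio: normal with SD 0.9, independent of baseline, mean -0.965 (INJ) and -2.081 (BIO). Check against ln 0.25 = -1.386: (-1.386 + 0.965)/0.9 = -0.47 gives 32%; (-1.386 + 2.081)/0.9 = 0.77 gives 78%.
- The measure has correlation ρ with the underlying log baseline. Its correlation with the diary count is lower, 0.21-0.23 when ρ = 0.3.
- Least squares with treatment in every model; 2,000 trials per cell.

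**False positives at nominal 5%: no effect on percent reduction, n = 170** (range over the three baseline spreads)

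| ρ | Absolute change | Absolute change + baseline | Percent change | Log ratio |
|---|---|---|---|---|
| 0.1 | 7-11% | 4-5% | 4-5% | 5-6% |
| 0.2 | 15-27% | 6-7% | 6% | 5-6% |
| 0.3 | 28-50% | 6-7% | 5% | 4-6% |
| 0.5 | 59-86% | 10% | 5-6% | 6% |

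With n = 80, absolute change without baseline gives 6-7% (ρ = 0.1), 15-29% (0.3) and 36-66% (0.5).

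**Power for a real effect of -0.25 in log rate ratio per SD** (exp(-0.25) = 0.78, a 22% lower rate), n = 170

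| ρ | Absolute change | Absolute change + baseline | Log ratio |
|---|---|---|---|
| 0 | 28-46% | 52-62% | 75-78% |
| -0.3 | 9-12% | 51-70% | 68-73% |
| +0.3 | 87-91% | 40-45% | 77-81% |

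**Additive truth** (a fixed number of episodes prevented whatever the baseline), no effect of the measure, ρ = 0.3 to 0.5. False positives are 5-7% for unadjusted absolute change. They are 25-80% for percent change and 33-92% for the unadjusted log ratio. Absolute change adjusted for baseline gives 9-26% at ρ = 0.3 and 17-62% at 0.5, because a two-week count is a noisy measure of the underlying rate.

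**The case against.** The strongest reply is that the plan never says the change is absolute. A general linear model can be fitted to percent change or a log ratio, and on those scales the false-positive problem disappears under proportional effects. That is correct. What then remains is an unstated scale, which still needs settling before analysis.

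Second, the false positives come mainly from the missing baseline covariate, not from the scale. This stands: adding baseline to absolute change brings them to 4-7% up to ρ = 0.3. Scale still matters for power (52-62% against 75-78% when the measure is unrelated to baseline).

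Third, proportional effects are assumed. Under additive effects unadjusted absolute change is the valid outcome and a log ratio misleads. This also stands, and it shapes the fix. Strict additivity is hard to sustain near the entry minimum, since a fixed reduction cannot exceed about 4 episodes per diary there. The additive runs also gave only 26-37% (BIO) and 12-18% (INJ) responders, below the plan's 78% and 32%. Neither fact rules out partly additive effects.

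Fourth, the stakes are limited. This is a secondary aim, and the predictor analysis beside it uses responder status, can include baseline frequency and covers most of the same physiology.

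A reader might infer that any measure correlated with baseline will look like a mechanism, and that real mechanisms will generally be missed. The figures support neither. At ρ = 0.1 the inflation is modest, and at ρ = +0.3 absolute change has more power than the log ratio, although part of that rejection rate is the severity association itself. Nor is benefit relative everywhere in the plan: FISS, FIQOL and PROMIS are analysed as score changes, and continence is an absolute state.

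**Conclusion.** The point holds as a gap in specification with material consequences under plausible conditions. The mechanistic model names no scale and lists no baseline FI frequency. If change is absolute and effects are roughly proportional, a pure severity marker is flagged in about 7-11% of trials at correlation 0.1 and 28-50% at 0.3. Power for a real effect unrelated to baseline is about 28-46%, against about 75% on a log scale. The loss is larger for measures negatively related to baseline and absent for positively related ones.

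These sizes rest on assumptions that the documents cannot confirm: proportional effects, the correlation of each measure with baseline, the spread of weekly episodes and the spread of response. The simulations treat each measure as a level. If changes in physiology are entered instead, their correlation with baseline frequency is unknown. The figures show what the planned wording permits; they are not a forecast for this trial.

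**What to change.** Amend the mechanistic paragraph of Section 8.3 to:

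- State the scale of the outcome and include baseline FI frequency. Preferably model the 3-month 14-day count with a negative binomial model, or the log ratio of 3-month to baseline counts (0.5 added to each), with log baseline count as covariate in either case.
- Keep treatment group and the planned interactions.
- Report absolute change, with and without baseline adjustment, as sensitivity analyses. Both are needed: in the additive runs only the unadjusted version held its error rate. A measure that appears on one scale only should be described as scale-dependent.
- Say whether physiological measures enter as baseline values or as changes.

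The cost is a few sentences, an extra sensitivity analysis, and effects reported as ratios instead of episodes. No further data are required, and the primary efficacy analysis does not change.
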